STUDY PROTOCOL

Nasal Intubation Using King Vision Video Laryngoscopy

[name]

(NCT03126344)

April 27, 2017

STUDY PROTOCOL

Title: A randomized controlled comparison of non-channeled King Vision, McGrath MAC video laryngoscope and Macintosh direct laryngoscope for nasotracheal intubation in patients with predicted difficult intubations.

Background: King Vision and McGrath MAC video laryngoscopes (VLs) are increasingly used. However, it remains unclear whether non-channeled King Vision or McGrath MAC VL, compared with conventional laryngoscope, provide shorter intubation time and a higher first success rate for NTI when used by experienced provider in management of predicted difficult intubation. It is also unclear whether non-channeled King Vision VL is superior to McGrath MAC VL when used for NTI.

Objective: To evaluate the performance of nasotracheal intubation in patients with predicted difficult intubations using non-channeled King Vision VL, McGrath MAC VL or Macintosh laryngoscope by experienced intubators.

Study Design: A single blind, three parallel arms, randomized controlled trial comparing NTIs using non-channeled King Vision VL, McGrath MAC VL and Macintosh DL in adults with predictors of difficult airways.

Subjects: Consecutive patients, between 18 and 60 years old with American Society of Anesthesiologists (ASA) classification of I or II, and requiring NTI for elective oral and maxillofacial surgery, were screened in the Preoperative Evaluation Unit of our institute.

Sample size: Based on the analysis of power analysis software, we take the type I error α as 0.05, the expected effect is 0.8, and the ideal test efficacy level is 0.8, then the minimum sample size of each group is 26. In order to reduce the loss of follow-up error, add 20% on this basis, then each group needs about 30 cases.

Recruitment method: Inpatients

Inclusion criteria: EGRI score 1–7.

Exclusion criteria: EGRI score > 7, history of reflux or diagnosed oesophageal disease, severe obstructive sleep apnea (OSA) and morbid obesity (body mass index > 40 kg/m²)

Study Methods:

1. Determine the subjects: select the patients who need nasotracheal intubation for elective operation, and determine 90 subjects strictly according to the inclusion and exclusion criteria, 30 in each group.
2. Group: Patients were randomly assigned to King Vision group, McGrath group or Macintosh group via a computer-generated randomization table: King Vision video laryngoscope group (group K, n = 30), McGrath MAC video laryngoscope group (group M1, n = 30) and Macintosh laryngoscope group (group M2, n = 30).

3. Anesthetic methods: the anesthetic methods of three groups were the same. Patients were asked which nostril was clearer. If both sides were equal and the surgeon had no objection, the right nostril was chosen.

No premedication was administered. Lactated Ringer's solution infusion was started intravenously to deal with the fluid loss from the overnight fast after entering the operating theatre. A standard preparation was then performed, including heart rate (HR), lead II ECG, SpO₂ (pulse oximetry), and end expiratory carbon dioxide. A Bispectral (BIS) index sensor was attached to the patient's forehead in conjunction with the BIS Monitor. Cannulation of right radial artery was performed under local anesthesia for invasive blood pressure monitoring.

All patients were preoxygenated by a facemask in the position of neutral. Prior to anesthesia induction, the nasal mucosa was well prepared with 1% tetracaine hydrochloride jelly for 2 min and five drops of ephedrine hydrochloride nitrofurazone (containing approximately 2 mg ephedrine) in all patients. Baseline hemodynamic data were recorded by an investigator after a stabilization period of 10 min.

The nasotracheal tube used was reinforced endotracheal tube (ETT, Safety-Flex with Murphy Eye, oral/nasal, Athlone, Ireland; ID 6.5mm in female and ID 7.0mm in male patients) and was well lubricated with 1 % tetracaine hydrochloride jelly. Dosing of induction medications was given at the discretion of the attending anesthesiologists. Induction agents included midazolam (0.02 mg/kg), propofol (1.5~2 mg/kg) and fentanyl (2 µg/kg). Upon loss of consciousness and jaw relaxation, manual ventilation was tested. If manual ventilation was available, cisatracurium besilate (0.15 mg/kg) was administered and post induction values were recorded 3 min after induction. Unsuccessful manual ventilation led to study exclusion.

The anesthesiologist tried to intubate when the Train of Four (TOF) count reached zero and BIS value decreased to 50. NTI was performed in a standard manner. First, a preformed ETT was inserted into the nostril and advanced to the posterior nasopharyngeal wall. Second, a laryngoscope blade was introduced into the mouth to expose the glottis. If it's necessary, the BURP maneuver (backward, upward, right-sided pressure) on the thyroid cartilage was attempted to obtain good glottis visibility. And ultimately, the ETT was inserted into the trachea with the aid of Magill's forceps, head flexion, or cuff inflation if necessary.

4. Observation outcome:

(1) Primary outcome: the intubation time

(2) Secondary outcome measures included time to expose the glottis (laryngoscopy time) and the view of glottis opening valued by Cormack-Lehane grade. A Cormack-Lehane grade IV was defined as laryngoscopy failure. A blinded investigator also recorded the hemodynamic changes (MAP, HR) during the procedure of NTI. The maximum values of invasive MAP were recorded. After successful intubation, the subjective sensation of the intubator (ease of device insertion, quality of view on display and ease of tube advancement) was graded as excellent, good, fair and poor. Other intubation parameters included incidences of bleeding or dental injury, number of assist maneuvers (use of BURP maneuver, Magill's forceps, or cuff inflation). Twenty-four hours after the procedure, a nurse anesthetist blinded to group assignment recorded the severity of sore throat and hoarseness.

Statistical analysis

Our sample size estimation was based on previous studies (11,23), in which the standard

deviations (SD) of intubation time were estimated as 8 and 13.7 seconds. To detect a intergroup difference of 10 seconds in intubation time with α of 0.05 and β of 0.8, we estimated that 30 patients would be enough for each group. To compensate for patients dropping out during the study, additional patients (10%) were added. The final sample size of 33 patients was in each group.

Mean (SD) or Median (IQR [range]) was used to describe the parametric data. The number (percentage) was used to describe nonparametric data. Statistical analyses were performed with Prism 5.0 for Windows (GraphPad Software, Inc., La Jolla, California, USA). Binary data for three groups were analyzed using chi-square test and each two groups were compared with chi-square segmentation method or Fisher's exact test as appropriate. One-way analysis of variance (ANOVA) with post-hoc Bonferroni's Multiple Comparison test was used to analyze parameter data for changes within groups. The Kruskal-Wallis ANOVA with post-hoc Dunn's test was used to analyze ordinal data. A p value less than 0.05 was considered as significant.

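### EGRI is scored before randomization but used only for eligibility; one prespecified covariate is a cheap gain in precision, with break-even at a correlation of about 0.11

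*Combined protocol and SAP*

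**What the plan says.** EGRI appears twice, both times under eligibility. The entry range is "Inclusion criteria: EGRI score 1–7" and the matching exclusion is "Exclusion criteria: EGRI score > 7, history of reflux or diagnosed oesophageal disease". Under Subjects, patients "were screened in the Preoperative Evaluation Unit of our institute", so the score should be available before allocation.

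Study Methods, item 2, assigns patients "via a computer-generated randomization table" and names no stratification factor. Item 4 makes intubation time the primary outcome.

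The Statistical analysis section takes its variability from earlier studies, in which the standard "deviations (SD) of intubation time were estimated as 8 and 13.7 seconds". It sizes for a 10 s difference and ends with "The final sample size of 33 patients was in each group", whereas Study Methods, item 1, has 30 per arm (90 in all). For continuous data it gives one-way ANOVA with a post-hoc Bonferroni test: "Multiple Comparison test was used to analyze parameter data for changes within groups". Taken literally, that describes within-group changes. It is also the only method given that fits a between-group comparison of mean times, and it has no covariate. Software: "Statistical analyses were performed with Prism 5.0 for Windows".

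**The concern.** The trial concerns patients whose intubation is expected to be difficult, and EGRI is the only difficulty score in the eligibility criteria. A score of that kind could plausibly predict how long intubation takes. If it does, leaving it out puts explainable between-patient variation into the error term of the primary comparison. It also leaves the observed device difference exposed to whatever EGRI imbalance arises by chance in three small arms with no stratification named.

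Power is what is at stake, and at the larger stated SD there is little to spare: the 30 per arm was sized at alpha 0.05, while the pairwise tests use a Bonferroni correction.

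**Working it through.** **Inputs from the documents.** Difference 10 s; SD 8 or 13.7 s; alpha 0.05; 30 or 33 per arm; three pairwise comparisons with Bonferroni, so 0.05/3 each.

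**Assumptions.** Tests are two-sided. The stated β of 0.8 is read as power 0.8. The EGRI effect is linear with a common slope, and residuals are roughly normal. Every r is an assumed correlation within the 1 to 7 range; that restriction may lower it.

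**The plan's own sample size.** n = 2(1.960 + 0.842)² × 13.7² / 10² = 29.5, so 30 per arm, and 30 × 1.10 = 33. The stated figures therefore follow from the larger SD at alpha 0.05 with no multiplicity correction. With SD 8 the same formula gives 10.05, so 11.

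**Formulas** (N = 3n, noncentral t):
- Unadjusted: SE = SD × √(2/n), df = N − 3.
- Adjusted: SE = SD × √(1 − r²) × √[(2/n)(1 + 1/(N − 5))], df = N − 4. The 1/(N − 5) term is the average cost of estimating the slope.

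**Break-even.** Setting (1 − r²)(1 + 1/(N − 5)) = 1 gives r = √(1/(N − 4)), which is √(1/86) = 0.108 at N = 90 and √(1/95) = 0.103 at N = 99. Allowing also for the lost degree of freedom, power breaks even at 0.110 and 0.104. A simulation of 40,000 trials at N = 90 and r = 0.108 gave an estimated-variance ratio of 1.000.

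**Pairwise power for 10 s, SD 13.7, alpha 0.05/3:**

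| Analysis | 30 per arm | 33 per arm |
|---|---|---|
| Unadjusted | 65.0% | 70.1% |
| Adjusted, r = 0 | 64.4% | 69.5% |
| r = 0.1 | 64.9% | 70.0% |
| r = 0.2 | 66.5% | 71.6% |
| r = 0.3 | 69.3% | 74.2% |
| r = 0.4 | 73.3% | 78.1% |
| r = 0.5 | 78.7% | 83.1% |

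Reaching 80% needs r of about 0.52 (30 per arm) or 0.44 (33). Put as sample size, 80% needs 41 per arm unadjusted, 38 at r = 0.3, or 31 at r = 0.5.

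**Equivalent sample size.** n / [(1 − r²)(1 + 1/(N − 5))] with n = 30 gives 29.7, 32.6 and 39.5 per arm at r = 0, 0.3 and 0.5.

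**Bonferroni interval half-width, 30 per arm:**
- SD 13.7: 8.64 s unadjusted; 8.69, 8.29 and 7.52 s adjusted at r = 0, 0.3 and 0.5.
- SD 8: 5.04 s unadjusted; 5.07, 4.84 and 4.39 s adjusted.

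**Power at SD 8.** 99.1% (30 per arm) or 99.5% (33) unadjusted, so less than 1 point can be gained.

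**Slope with one device only** (simulation, 30 per arm, SD 13.7, EGRI assumed uniform on 1 to 7). Pairs that include that device go from 65.1% to 65.1% at r = 0.3 in that arm, and from 65.2% to 66.2% at r = 0.5. The other pair changes by −0.3 and +0.4 points. Type I error, nominal 1.67%, was 1.53% in the r = 0.5 case and 1.68% with a common slope at r = 0.3.

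**Chance imbalance.** The probability that at least one of the three pairs differs by more than 0.5 SD in mean EGRI is 12.8% (30 per arm) or 10.5% (33). Such a difference shifts the unadjusted estimate by 0.5 × r × 13.7, which is 0.7, 2.1 or 3.4 s at r = 0.1, 0.3 or 0.5.

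**The case against.** The strongest reply is that nothing here is wrong. Unadjusted ANOVA is a legitimate choice, and the case for changing it rests on a correlation that no document supplies. The break-even of 0.11 marks only where the loss stops: at r = 0.2 the gain is 1.5 points (65.0% to 66.5%), and a useful gain needs about 0.3. The visible gains also require the larger of the two stated SDs. In a trial of whether video devices help when difficulty is expected, EGRI may matter more with one device than another, and the gain then nearly vanishes. The plan allows medians and IQRs, so skewed times are foreseen, while these figures assume a normal linear model.

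All of this stands as a limit on the benefit. Two narrower points also stand:
- Correcting a chance imbalance is not a benefit on top of the variance reduction. A single pairwise imbalance has SD √(2/30) = 0.26 EGRI SDs, worth about 0.26 × 0.3 × 13.7 = 1.1 s at r = 0.3, and the unadjusted standard error already includes it.
- That EGRI defines predicted difficulty is inferred from the title and the entry criteria; the documents do not say so.

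None of this makes the covariate costly. The worst case shown is a loss of about 0.6 power points, and adjustment did not raise the type I error to any material degree in either case simulated.

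**Conclusion.** The point holds as a low-cost improvement, conditional on r. EGRI is obtained for every patient and is not used in the primary comparison. At SD 13.7 and 30 per arm, adjusting loses 0.6 points of pairwise power if EGRI is unrelated to intubation time. It gains about 4 points at r = 0.3 and about 14 at r = 0.5. At 33 per arm the figures are a loss of 0.6 and gains of about 4 and 13. At SD 8 the power gain is negligible, although intervals still narrow (5.04 to 4.84 s at r = 0.3, 30 per arm).

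These figures rest on a linear common slope, roughly normal residuals and an assumed r. The fall from 79.8% power at alpha 0.05 to 65.0% at 0.05/3 is a separate sizing problem, which this adjustment only partly offsets.

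**What to change.** In the Statistical analysis section, define the primary analysis of intubation time explicitly as a between-group ANCOVA: device as factor, EGRI score as one linear covariate, Bonferroni-adjusted pairwise differences in adjusted means, and 95% intervals. Keep the unadjusted one-way ANOVA, in the same patients, as a sensitivity analysis.

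Fix this before outcome data are examined. If they have already been examined, keep the unadjusted analysis primary and report the ANCOVA as supportive.

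Check that Prism 5.0 fits this model, and name another package if it does not. Stratified randomization, a log-time fallback for skewed times and a device-by-EGRI interaction are optional additions.

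The cost is about two sentences, one degree of freedom and possibly a change of software. No new measurement or visit is needed.

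### MAP and HR changes have no named pre-stimulus reference: the post-induction reading is clock-timed, the attempt is triggered by TOF and BIS, and the stated ANOVA has no covariate

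*Combined protocol and SAP*

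**What the plan says.** Study Methods, item 3 (Anesthetic methods), schedules two readings before the attempt. The first is awake: "Baseline hemodynamic data were recorded by an investigator after a stabilization period of 10 min". The second follows induction: "post induction values were recorded 3 min after induction". The values are not listed, but in context they are haemodynamic. The moment from which the 3 minutes run is not defined.

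The same item starts the attempt on a different rule: "The anesthesiologist tried to intubate when the Train of Four (TOF) count reached zero and BIS value decreased to 50". The first step of the attempt is nasal, ahead of the blade: "First, a preformed ETT was inserted into the nostril and advanced to the posterior nasopharyngeal wall".

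Item 4 (Observation outcome) gives the secondary outcome: "A blinded investigator also recorded the hemodynamic changes (MAP, HR) during the procedure of NTI". It adds: "The maximum values of invasive MAP were recorded". No maximum HR is mentioned, and no reference reading for change is named.

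The Statistical analysis section has one sentence on continuous data: "One-way analysis of variance (ANOVA) with post-hoc Bonferroni's Multiple Comparison test was used to analyze parameter data for changes within groups". It mentions no covariate and does not define a change score. It does not describe a between-device analysis of MAP or HR.

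**The concern.** A pressor response is a rise from the state just before stimulation. Here the scheduled post-induction value is fixed to the clock, while stimulation starts when each patient reaches the TOF and BIS criteria. The time to reach them can vary, partly because "Dosing of induction medications was given at the discretion of the attending anesthesiologists". In a patient who reaches them late, the 3-minute value is out of date if pressure is still moving. The order is also not guaranteed, since nothing requires the 3-minute reading to be complete before the tube is passed.

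Two things are at stake. The reported rise in MAP or HR may mix the stimulus with continuing induction effect. And with about 30 patients per arm, a device comparison that leaves out the patient's own pre-stimulus level gives up precision that the monitoring already in place could supply.

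**Working it through.** The documents give no SD, correlation, drift or target difference for MAP or HR, so there is no stated figure to reproduce. Every haemodynamic value below is an assumption. The sample size used is 30 per arm, the figure in the Statistical analysis section before its dropout allowance.

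**1. Timing, side by side.**
- Awake baseline: after 10 min of stabilisation, before induction.
- Post-induction value: 3 min after induction.
- Start of attempt: TOF count zero and BIS 50, with no clock time.
- Between trigger and nasal tube: no reading specified.

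The interval from the second reading to the first stimulus is therefore not fixed, and the plan does not say that it is recorded.

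**2. Absolute response.** Assume a gap uniform between 0 and 4 min, a mean drift of −3 mmHg/min and a true mean rise of 25 mmHg. The mean gap is (0 + 4)/2 = 2 min and the mean drift is 2 × (−3) = −6 mmHg, so the rise measured from the 3-minute value averages 25 − 6 = 19 mmHg. Size and sign follow the assumed drift.

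**3. Device contrast.** A simulation of 8,000 three-arm trials used the same gap and drift, a 3-minute MAP SD of 10 mmHg, extra drift SD of 3 and response SD of 8. Each outcome was compared between arms by one-way ANOVA.

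| Outcome | Type I error | Estimate of a true 8 mmHg effect | Power |
|---|---|---|---|
| Raw maximum | 4.9% | 8.0 | 63% |
| Maximum minus 3-min value | 5.0% | 8.0 | 94% |
| Maximum minus just-before value | 4.8% | 8.0 | 98% |

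No analysis is biased. Most of the gain comes from using any pre-stimulus value, and correct timing adds a little more. These inputs favour adjustment. The just-before variance is 10² + 3² × 4²/12 + 3² = 121, and that of the maximum is 121 + 64 = 185. The implied correlation with the maximum is √(121/185) = 0.81 for the just-before value and 10/√185 = 0.74 for the 3-minute value.

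**4. Precision over a wider range.** With correlation r, ANCOVA leaves 1 − r² of the unadjusted variance, and the equivalent sample multiplier is 1/(1 − r²). For raw maximum MAP at two-sided α 0.05 and 80% power, the detectable difference is (1.96 + 0.84) × √(2/30) = 0.72 SD. Multiply by √(1 − r²) for ANCOVA, or by √(2(1 − r)) for a change score with equal SDs.

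| r | Variance cut, r² | Equivalent extra patients | ANCOVA detects | Change score detects |
|---|---|---|---|---|
| 0.3 | 9% | 10% | 0.69 SD | 0.86 SD |
| 0.5 | 25% | 33% | 0.63 SD | 0.72 SD |
| 0.7 | 49% | 96% | 0.52 SD | 0.56 SD |

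At r = 0.3 a change score is worse than the raw maximum, whereas ANCOVA is better in every row.

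**5. Cost of the mistimed reading alone.** Assume SDs of 15 mmHg (maximum) and 12 mmHg (just-before), correlation 0.6, and independent drift of SD 8 mmHg in the 3-minute value.
- Change-score SD without drift: √(225 + 144 − 2 × 0.6 × 15 × 12) = √153 = 12.4. With drift: √(153 + 64) = 14.7, close to the raw SD of 15.
- Correlation falls from 0.60 to 0.6 × 12/√(144 + 64) = 0.50.
- ANCOVA then leaves 1 − 0.50² = 0.75 of the variance instead of 1 − 0.60² = 0.64, and the detectable difference grows by √(0.75/0.64) = 1.08, about 8%.

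**The case against.** The strongest reply is that the trial asks about devices, and the device contrast is sound. Item 2 randomises patients, and item 3 gives all three groups the same anaesthetic method. Readings and trigger are common to all arms and, in the order written, precede device use, so gap and drift are independent of arm in expectation. This stands. A reader might infer that the pressor response has no valid reference, or that the device effect is contaminated. The documents do not support that: the 3-minute value, taken before the tube, is a fair reference between arms and a usable covariate.

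A reader might also infer that the device comparison disregards the pre-stimulus value. The plan is silent instead. The ANOVA sentence concerns change within groups and neither uses nor excludes an earlier reading. The savings above are therefore measured against an unadjusted ANOVA of the maximum, which is an assumed comparator.

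Nor do the documents show that any patient is read during laryngoscopy. No onset times are given, and the text places the reading before the attempt. It is a possibility that the plan leaves open.

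Two further points stand. MAP and HR are recorded during the procedure, with arterial pressure monitored invasively, so a suitable value may well exist, but the plan does not designate one. And a reference taken before nasal passage captures the response to the whole procedure, without separating the blade from the tube.

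**Conclusion.** The concern holds in a limited form and merits a change to the plan. The reference for haemodynamic change is undefined, no reading is tied to the start of stimulation, and the stated method for continuous data has no covariate. Between devices the consequence is lost precision without bias: 9% to 49% of the variance for assumed correlations of 0.3 to 0.7. The mistiming itself is the smaller part, about 8% on the detectable difference in the one case worked. The absolute response can be distorted, by 6 mmHg in the illustration. These sizes rest on assumed correlations, SDs, gaps and drifts. Only secondary outcomes are involved, and intubation time is untouched.

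**What to change.** - Take MAP and HR from the running arterial line and ECG once the TOF and BIS trigger is met and just before the tube enters the nostril, with a time stamp. Name this value as the reference for haemodynamic change.
- Record maximum HR as well as maximum MAP.
- Compare maximum MAP and maximum HR between the three devices by ANCOVA with that patient's pre-stimulus value as covariate, keeping the planned Bonferroni pairwise comparisons.
- If the value is missing, use the 3-minute post-induction value as covariate, provided its time stamp precedes the tube.
- Record the time from the 3-minute reading to the attempt.

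The cost is one extra time-stamped reading from monitoring already in place, one degree of freedom and a sentence of analysis text. Induction, the trigger and the intubation technique stay as they are.

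### Maximum MAP is read over a procedure-bound window of no fixed length, so a faster device can show a lower maximum with an identical pressor response

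*Combined protocol and SAP*

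**What the plan says.** Section 4, Observation outcome, item (2), says that a blinded investigator "recorded the hemodynamic changes (MAP, HR) during the procedure of NTI". The next sentence adds: "The maximum values of invasive MAP were recorded". Neither sentence says when recording starts or stops.

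The steps of the procedure are set out at the end of section 3, Anesthetic methods. They begin with the nose: "First, a preformed ETT was inserted into the nostril and advanced to the posterior nasopharyngeal wall". Laryngoscopy and passage of the tube into the trachea follow.

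The other haemodynamic time points are both in section 3 and both precede intubation: a baseline before induction, and "post induction values were recorded 3 min after induction". No reading at a fixed time after tube placement is planned.

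Item (1) of section 4 reads "Primary outcome: the intubation time", without start or stop points. The Statistical analysis section sizes the trial as follows: "To detect a intergroup difference of 10 seconds in intubation time with α of 0.05 and β of 0.8". It plans one-way ANOVA with Bonferroni comparisons for continuous data and mentions no adjustment for how long the procedure lasted.

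**The concern.** For any given pressure trace, the maximum over a longer window cannot be lower than the maximum over a shorter one that starts at the same point. If recording ends with the procedure, a device that takes longer gives its patients a longer observation time. Where pressure is still climbing when the tube goes in, the later part of the rise is lost, and it is lost sooner in the faster arm. The artefact therefore has one direction: it can only lower the faster arm's value.

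Neither randomisation nor blinding of the recorder removes this, because the length of the window is itself a consequence of the assigned device. What is at stake is the reading of a MAP difference: a lower maximum could mean a gentler device or only a shorter look at the same response, and the plan gives no means of telling the two apart.

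**Working it through.** **The plan's own figure.** The documents give no figure for MAP. The one related figure is the sample size for intubation time. Reading the stated β of 0.8 as power 0.8, with two-sided α 0.05 (sidedness is not stated):

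n per group = 2 × (1.96 + 0.84)² × SD² / δ²

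- SD 13.7 s, δ 10 s: 2 × 7.85 × 187.69 / 100 = 29.5, so 30, as stated.
- SD 8 s: 2 × 7.85 × 64 / 100 = 10.05, so 11.

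The stated 30 therefore rests on the larger SD. This confirms 10 s and 13.7 s as the plan's working values for intubation time, and they are used below.

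**Simple model.** Give both arms the same curve: a linear rise of 25 mmHg that peaks at time tp. The window closes at time T. The recorded rise is

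25 × min(T, tp) / tp

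T is Normal with SD 13.7 s, floored at 5 s, and the arm means are 10 s apart. The 25 mmHg, the curve, tp and the mean times are assumptions. Only the 10 s and the SD come from the documents.

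If every window closes before the peak, the difference in means is 25 × 10 / tp: 4.2 mmHg at 60 s, 2.8 at 90 s and 2.1 at 120 s. Allowing for the spread of T:

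| Mean T, fast v slow (s) | tp (s) | Difference in recorded maximum (mmHg) |
|---|---|---|
| 30 v 40 | 60 | 4.0 (12.5 v 16.5) |
| 30 v 40 | 90 | 2.7 (8.4 v 11.1) |
| 30 v 40 | 120 | 2.1 (6.3 v 8.3, before rounding) |
| 45 v 55 | 20 | 0.2 |
| 45 v 55 | 30 | 0.6 |
| 60 v 70 | 45 | 0.4 |
| 60 v 70 | 30 | under 0.1 |

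With the plan's smaller SD of 8 s, the first three rows become 4.2, 2.8 and 2.1, so the choice of SD matters little there.

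**Fuller simulation.** This used 30 patients per arm, SD of T 10.85 s (the midpoint of 8 and 13.7), between-patient SD 12 mmHg, within-patient SD 3 mmHg, the same 25 mmHg response in both arms, a two-sample t-test (a simplification of the planned three-arm ANOVA) and 600 runs per setting.

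- Peak clearly after the faster arm's mean window closes: the faster arm's maximum is lower by 2.7 to 4.7 mmHg, and the false-rejection rate is about 10% to 25% against a nominal 5%.
- Peak at about the mean close of that window: 1.8 to 2.5 mmHg, rejection 7% to 10%.
- Peak inside the window, or a flat response: 0.1 to 0.7 mmHg in most settings, rejection 3% to 6%. The exception is a peak at 20 s with a 30 s mean window, where the margin is only 10 s: 1.7 mmHg.
- Common fixed window (180 s, for illustration): the true difference is zero by construction. The runs gave −0.03 to 0.36 mmHg and rejection of 4% to 6%, with a Monte Carlo standard error of about 0.15 mmHg and 1 percentage point.

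**The case against.** Three stronger readings are tempting, and the documents support none of them.

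- **That the MAP window is the primary outcome under another name.** Neither interval is defined. The procedure as described starts with nasal passage of the tube, before the blade enters the mouth, so the two need not coincide. The sentence on the maximum states no window of its own; the link comes from the sentence before it. What stands is that the procedure includes laryngoscopy and tracheal insertion, so a slower device would be expected to lengthen it.
- **That the trial expects a 10 s difference between devices.** Ten seconds is the difference the trial is sized to detect. The Background calls it unclear whether the video devices shorten intubation.
- **That the faster device will show a lower maximum.** This follows only if pressure is still rising when the window closes. A range built only on peaks after both mean intubation times would leave out the settings where almost nothing happens.

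A fourth argument is fair and stands in part. Longer laryngoscopy may be a longer stimulus, so a higher maximum in a slower arm could be a genuine effect of that device. A common window does not remove this, nor should it. It removes only the unequal observation time.

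On weight, this is one of many secondary measures. The stated objective does not name haemodynamics, and no sample size rests on them.

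**Conclusion.** The concern holds in a conditional form. The plan takes maximum MAP, and HR changes, over a window with no fixed length that may vary with intubation time and so by device. If MAP is still rising at the close of the window, the faster arm can show a lower maximum with an identical response.

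For an assumed 25 mmHg linear rise and a 10 s gap in mean time, the artefact is about 0 mmHg when the peak falls well inside the window and about 4 mmHg when it falls after it (up to 4.7 in the least favourable simulated setting). The time to peak decides which applies, and the documents do not give it. Whether the bias is material in this trial therefore cannot be settled from them.

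The primary comparison of intubation time is untouched. The change is still worth making: if the window is procedure-bound, the MAP comparison is open to this bias, and if it is not, the plan does not say what it is.

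**What to change.** In section 4, item (2), replace the procedure-bound period with one fixed observation window for every patient in all three arms:

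- **Anchor:** the start of nasotracheal intubation, meaning insertion of the tube into the nostril. An anchor at blade insertion would leave out the first step of the procedure.
- **Length:** long enough to extend past tube placement in essentially all patients, for example 5 minutes. Flag and report any intubation that outlasts it.
- **Measures:** maximum MAP and maximum HR within that window.
- **Comparison:** between devices, on the rise from the post-induction value that section 3 already records.

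The arterial line and ECG are already in place, so the cost is wording and a few more minutes of recording. There are two limits. Some post-intubation events will fall inside the window, with somewhat more post-intubation time in the faster arm. And because any true effect of longer laryngoscopy is kept, a remaining MAP difference may still partly reflect intubation time and should be reported with that caution.
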